6 STUDY INTERVENTIONS

6.1 Study Interventions

Control group (usual care). During the treatment phase of the study, each participant randomized to control will receive usual care from SLAAA, which includes annual NAPIS evaluation (in home) and individualized referrals to services based on identified need. Referrals are generated by case managers or SLAAA staff based on the annual assessment or if older adults (or their family members) call and request a referral for services.

Procedures for intervention (treatment). Participants who are randomized to treatment will receive usual care plus the home-modification (home-hazard removal) intervention. The intervention, based on a competence/press theoretical framework,⁹⁶ will be provided by registered and licensed OT. The intervention will be delivered via a manualized intervention using a visit by visit checklist. Home modifications⁷⁹ include a 2-hour home assessment conducted by an OT in the participant’s home using the WeHSA. A comprehensive clinical assessment will be performed on each participant to determine functional limitations that may interact with hazards in the home and result in a fall. Environmental hazards and unsafe behaviors will be identified. A barrier-removal plan will be provided to the older adult. The OT will facilitate home modifications through housing services programs and provided follow-up 2 weeks after the initial home visit to ensure that the participant adopted the recommended modifications. It is anticipated that 2-3 visits of 90 minutes each will be provided. At about 6 months participants will receive a booster session (in home visit by an OT) to reevaluate performance in the home and modify the intervention plan as needed.

Interventionist Training

Each interventionist will receive a 3 hour didactic training and additional 2 hours of guided self-directed learning.

5.2 Process Evaluation

We will evaluate a set of implementation outcomes distinct from clinical treatment outcomes⁹⁹ that are relevant for decision makers and important for implementation and dissemination of the intervention. The components and data sources of the process evaluation are presented in Table 1. We will conduct a process evaluation to understand the fidelity, safety, cost, and quality of the intervention.¹⁰⁰ We will monitor recruitment metrics for all eligible participants, including demographic characteristics, enrollment status, and reason for decline. We will determine the fidelity of the intervention by determining whether the intervention was delivered as planned and

calculating the dose of the intervention received by both groups (number of minutes and number of sessions delivered). OTs will rate adherence at the final visit as the number of recommendations implemented per recommendations suggested.⁶ Long-term adherence will be calculated as the number of recommendations used at 12 months per recommendations suggested. We will examine reasons for abandonment of strategies to inform the final program. We will explore the safety of the intervention by determining the rate and severity of falls (calculated with an algorithm).¹⁰¹ Environmental modifications are provided through a patchwork of services in the US; therefore, reliable cost data are not available. We will track the cost of service provision (in the treatment group). We will record OT time to provide services (direct and indirect)¹⁰² and costs of equipment issued to participants. Costs of contracting services will include installation (labor and materials) and maintenance or repair during follow-up. All OT time will be recorded using current procedural terminology codes. The hourly wage of the contractor will be estimated using wage rates for the St. Louis area as reported by the U.S. Bureau of Labor Statistics.¹⁰³ The cost of all materials will be captured from invoices. Costs will be estimated from the payor perspective (e.g., Medicare allowable costs will be used to estimate covered clinical encounters).¹⁰⁴

[figure not shown]
7 STUDY PROCEDURES

7.1 Schedule of Evaluations

7.2 Overview

Assessments will be conducted at baseline and 6 months after intervention for participants in the treatment group and will occur in participants' homes. For those in the control group, no 6 month assessment will occur. A 12 month phone follow up will occur for all participants.

Treatment

Control

7.3 Description of Evaluations

7.3.1 Screening Evaluations

7.3.1.1 Short Blessed Test (SBT). The SBT[61] will be used to screen for severe cognitive impairment. The SBT has good validity for older adults[61] and correlates well with the Mini-Mental State Exam[62]. This brief, six-item questionnaire assesses cognition, memory, and orientation. Incorrect items are scored as the product of the number of errors made and a weighting factor; the sum of incorrect item scores comprises the total score. Total scores range from 0-28; scores of 10 or more are consistent with dementia and other cognitive difficulties. Individuals who receive a SBT score 10 or more will not be allowed to participate in the proposed study.

7.3.1.2 Any self-report of fear of falling in past year.

7.3.1.3 Falls in past year. Any report of falls in the previous year will be an automatic inclusion.

7.3.2 Enrollment, baseline, randomization

7.3.2.1 Enrollment

Informed Consent Process. All elements of consent will be reviewed with older adults prior to enrolling in the study, including the purpose of the study, risks, benefits, alternatives to the study, how confidentiality will be maintained, the PI's contact information, no consequences to withdrawal, and how study results will be shared. All study staff have undergone IRB training. In addition, all staff members have participated in cultural competence training and are trained to interview older adults. All staff members are trained to obtain assent, which is particularly important for older adults with low vision, low literacy levels, or limited English proficiency. All study documents are available in multiple formats, are developed in 16-point Arial font, and are written in plain language. All informed consent documents are reviewed by the laboratory advisory board of older adults (involved in the design of the study) to ensure clarity for older adults.

Steps to understand the elements of informed consent. Written informed consent to participate in the study will be obtained before any test or measurement is performed. Eligibility will be confirmed prior to enrollment. All potential participants will be screened using a script by the coordinator. Screening will take place in person or over the phone. Potential participants will be given a copy of the large-print informed consent document and a study review sheet written at the appropriate reading level to review. During screening, all participants (1) will have a detailed, plain-language explanation of the study and what is expected of them; (2) will discuss potential problems that could interfere with participation; (3) will have their questions answered; and (4) will receive a plain-language summary of the study and contact information for the PI and study coordinator. Consent will occur during the first home assessment visit. The consent form will be signed by a witness and stored in the office of the PI under double locks. Participants will be advised in the consent form that there is a possibility that their medical research record, including identifying information, may be inspected and photocopied by

officials of Federal or state government agencies and the Washington University Human Research Protection Office.

Enrollment. Enrollment is defined as the date all of the screening criteria are met and the individual agrees to participate. The enrollment date will be recorded on a case report form.

7.3.2.2 Randomization.

Participants will be allocated using a 1:1 ratio via randomization sequences generated a priori using a computerized formal probability model. The allocation ratio will be maintained at periodic intervals. Groups will be balanced with regard to race (self-reported African American or “other”) and sex. Randomization sequence concealment will be achieved by the Research Electronic Data Capture (REDCap) system.⁸¹ The study coordinator will verify that all eligibility requirements are satisfied and then elicit treatment assignment prior to baseline assessment.

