5 SELECTION AND ENROLLMENT OF PARTICIPANTS

5.1 Inclusion/Exclusion Criteria

Inclusion criteria: 1) aged 65 years or older; 2) self-report of one previous fall or more in the preceding 12 months or self-report as “worried about falling;” and currently receiving services from SLAAA.

Exclusion criteria: 1) residents of nursing homes; 2) individuals with severe cognitive impairment who are unable to give consent to participate (as determined by a score of greater than 10 on the SBT for memory¹⁰)

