Short Michigan Alcoholism Screening Test – Geriatric Version (S-MAST-G). The S-MAST-G^[58] will be used to screen for the presence of an alcohol problem in potential participants. The S-MAST-G has been validated for the older adult population^[59]. Potential participants will answer 10 yes/no questions about their alcohol consumption in the past year; two or more “yes” responses indicate a likely alcohol problem..

Geriatric Depression Scale Short Form (GDS-SF). The GDS-SF^[60] will be used to assess depression levels in participants. The GDS-SF is a 15-item self-report questionnaire specifically designed and validated with the older population, and correlates highly with the original 30-item GDS ($r=.84$)^[60]. Participants answer yes-or-no questions about their feelings in the past week. Total scores range from 0 to 15, and scores of 5 or more indicate probable depression.

Short Blessed Test (SBT). The SBT^[61] will be used to screen for severe cognitive impairment. The SBT has good validity for older adults^[61] and correlates well with the Mini-Mental State Exam^[62]. This brief, six-item questionnaire assesses cognition, memory, and orientation. Incorrect items are scored as the product of the number of errors made and a weighting factor; the sum of incorrect item scores comprises the total score. Total scores range from 0-28; scores of 10 or more are consistent with dementia and other cognitive difficulties. Individuals who receive a SBT score 10 or more will not be allowed to participate in the proposed study.

Prescription medications. A medication inventory will be collected.

Performance Oriented Mobility Assessment (POMA). Mobility and balance will be assessed using the Performance Oriented Mobility Assessment (POMA)^[63], a task-oriented gait and balance assessment that has been validated for the older adult population.

Strength, and range of motion of the upper extremity. Strength and range of motion of the upper extremity will be assessed using group muscle tests and goniometry and scored as within normal limits, within functional limits, or impaired^[64]. Strength of the dominant hand will be assessed using a dynamometer.

Pelli-Robson. We will measure visual contrast sensitivity using the Pelli-Robson test^[65]. We will score participants’ binocular contrast sensitivity letter by letter.

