7.4.6 Cost

The cost of the treatment will be measured by tracking cost of modifications and adaptive equipment for each participant. This will be tracked using the Invoice Form which includes both

costs from the contractor as well as costs of any equipment ordered from a medical supply company or obtained from a community resource (medical equipment lending program). The total amount of money spent on each person will be tracked on this form.

7.5 Overview of study assessments by time point.

	Phone Screening	Consent visit	Baseline assessment	Treatment session (tx group only)	Follow-up months 1-12	5 month phone call (tx group only)	6 month Booster in home (tx group only)	12 month phone call
Consent		x						
Calendar Questionnaire		x						
Demographics		x						
WeHSA			x	x			x	
SMAST-G			x					
GDS		x						
SBT	x							
Medication		x						
ROM			x					
Strength			x					
Grip Strength			x					
Near Visual Acuity			x					
Contrast Sensitivity			x					
POMA			x					
Falls			x	x	x			x
OARS			x					x
FES		x						x
PROMIS		x						x
Falls behavioral Scale		x						x
Fidelity to treatment (visit by visit grid)			x	x			x	
Time (Dose), Completion of Session, Cost				x			x	
Adherence						x	x	x

*randomization before T1

*both groups will send in monthly fall journal information

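### The excluding cognitive test (SBT) is marked at phone screening, before the written consent that must precede any test, and unreconciled wording leaves open that it could bar someone already randomised

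*Combined protocol and SAP*

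**What the plan says.** On consent, section 7.3.2.1 says "Written informed consent to participate in the study will be obtained before any test or measurement is performed" and "Consent will occur during the first home assessment visit". Section 5.2 agrees that consent is taken at the baseline home visit. Section 7.3.2.1 also says "Screening will take place in person or over the phone".

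On the SBT, section 7.3.1.1 lists it as a screening evaluation that "will be used to screen for severe cognitive impairment", and a score at or above the limit bars participation. The 7.5 table has a single SBT mark, under phone screening. Section 7.3.2.3 (Baseline Assessment) describes the SBT again and ends with the same bar: "Individuals who receive a SBT score 10 or more will not be allowed to participate in the proposed study".

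On assignment, section 7.3.2.2 has the coordinator check that every eligibility requirement is met and then "elicit treatment assignment prior to baseline assessment". A footnote to the 7.5 table reads "randomization before T1", with T1 undefined. Section 5.2 says the reverse: the coordinator verifies eligibility and obtains the assignment after baseline assessment. The design outline in section 4 also lists baseline before randomisation.

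**The concern.** There are two conflicts, of different strength.

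The first is between the consent rule and the schedule. The SBT is a scored six-item test whose result excludes people. If it is given by phone before the consent visit, it is a test performed before written consent, against the protocol's own protection.

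The second is between the SBT text and the timing of randomisation. If 7.3.2.3 and 7.3.2.2 are both followed literally, the arm is drawn and an excluding test comes afterwards. Someone who passed at screening, was assigned and then scored at or above the limit would be barred. The groups compared would then no longer be the groups randomised. Those lost would be the more cognitively impaired, and if testing or scoring were influenced by knowledge of the arm, the loss could differ between arms.

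No section says what happens to such a person. Section 9 covers discontinuation for adverse events and voluntary withdrawal. The Data Analyses section gives censoring rules for people who do not fall and for moves to a nursing home. Neither states that all assigned participants are analysed.

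**Working it through.** This is mainly a check of text against text. There are two candidate times for the SBT and two for randomisation, so four combinations:

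1. **SBT at phone screening (7.5, 7.3.1.1), randomisation after baseline (sections 4 and 5.2).** Nobody is barred after assignment. The consent rule in 7.3.2.1 is broken.
2. **SBT at phone screening, randomisation before baseline (7.3.2.2).** The result is the same: no removal after assignment, consent rule broken.
3. **SBT at baseline (7.3.2.3), randomisation after baseline.** Consent precedes the test and the test precedes assignment, so neither problem arises. But 7.5 shows no SBT at the consent or baseline visit, and 7.3.2.2 is contradicted.
4. **SBT at baseline, randomisation before baseline.** The excluding test follows assignment. Because 7.3.2.2 requires eligibility to be verified first and the SBT is an exclusion criterion in 5.1, this works only if the SBT is given twice.

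No combination satisfies every section. The consent conflict arises whenever the 7.5 schedule is followed. Removal after assignment arises only in combination 4.

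**Scale of combination 4, for illustration.** Inputs from the sample size section: event-free proportions 0.39 (control) and 0.58 (intervention), 300 participants, 20% attrition, two-sided 0.05, stated power 84%.

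- Hazard ratio = ln(0.58)/ln(0.39) = 0.5785, as stated.
- Evaluable = 300 × 0.8 = 240, or 120 per arm. Events = 120 × (0.42 + 0.61) = 123.6.
- Freedman's formula: power = Φ(√events × (1 − HR)/(1 + HR) − 1.96) = Φ(√123.6 × 0.4215/1.5785 − 1.96) = 84.3%, which reproduces the stated 84%. Schoenfeld's formula gives 86.0%, so Freedman's is used below.

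The documents give no rate of failure on a repeat SBT. Suppose a share r of the 300 is removed, equally in both arms and in addition to the 20% attrition. Events are then 123.6 × (1 − r):

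| r (assumed) | Removed | Events | Power |
|---|---|---|---|
| 0 | 0 | 123.6 | 84.3% |
| 3% | 9 | 119.9 | 83.2% |
| 5% | 15 | 117.4 | 82.5% |
| 10% | 30 | 111.2 | 80.4% |

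If the removals fell within the 20% already allowed for, power would not change.

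**The case against.** The strongest objection is that the SBT paragraph in 7.3.2.3 is not a second administration at all. It repeats 7.3.1.1 word for word. The section reads as an inventory of instruments: demographics, GDS, medications, FES-I, PROMIS and the falls behaviour scale are all described there, yet 7.5 ticks them at the consent visit. The authors reuse screening wording elsewhere too; the final evaluation in 7.3.4 still says that certain OARS scores qualify a person for the study, which cannot be a working rule at that point. In addition, 7.3.2.1 confirms eligibility before enrolment, and T1 in the footnote may mean the first treatment session. This largely stands. It is why removal after assignment can be called only a risk.

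A reader might go further and infer that the SBT is scheduled twice and that randomised people will be removed by staff who know the arm. The documents do not support that. The schedule shows one SBT. No section says who would give a baseline SBT or whether that person would know the allocation. The timeline does give one staff code to both baseline assessment and intervention delivery, but 5.2 promises a blinded evaluator for outcomes at baseline. Moreover, a bar applied identically in both arms to a score taken before treatment would cost numbers and narrow the population, without in itself favouring either arm.

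On consent, one can answer that 7.3.2.1 itself provides for scripted screening by phone, that cognition may need checking before consent is sought, and that an oral consent or waiver may exist in documents outside the protocol text. Each is plausible. None makes the consent sentence and the 7.5 table consistent as written.

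**Conclusion.** The consent conflict holds without qualification on the protocol text: written consent at the first home visit must precede any test, and the only scheduled SBT comes before that visit.

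The possibility of barring a randomised person holds conditionally. It requires that 7.3.2.3 be read as a real second SBT and that the 7.3.2.2 timing be followed over 5.2. The protocol neither requires that reading nor rules it out, and it has no rule for analysing a randomised person later found ineligible.

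The size is unknown. The drop in power from 84% to about 83% (3% removed) or 80% (10% removed) rests on assumed rates, equal removal in both arms, and removals additional to the planned attrition. The matter of substance is selective loss after allocation, which would bias the comparison only if testing, scoring or attendance differed by arm. The passages should be reconciled because the correction is cheap and closes off that route.

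**What to change.** - Give the eligibility SBT once, always before assignment: either at the consent visit straight after signature, or by phone under an oral screening consent. Amend 7.3.2.1 and the 7.5 table to match the choice.
- Delete the sentence barring participation from the SBT paragraph in 7.3.2.3. The bar remains in 5.1 and 7.3.1.1.
- Reconcile 5.2 with 7.3.2.2 on whether assignment is drawn before or after baseline assessment, and define T1 in the 7.5 footnote.
- State in the Data Analyses section that nobody is removed from the analysis after assignment because of an SBT score.

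The cost is protocol wording and one schedule cell. In practice it means either a script for oral screening consent or a home visit for the few who consent and then fail the test.

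While these sections are open, note that 5.1 excludes "as determined by a score of greater than 10 on the SBT for memory" whereas 7.3 bars a score of 10 or more. A score of exactly 10 is treated differently in the two places, and they must also be reconciled.

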4 STUDY DESIGN

To examine the effect of a home-modification (home-hazard removal) program, we will conduct a hybrid effectiveness/implementation trial of 300 older adults at risk for a fall who will be randomized to a home-hazard removal program or usual care and then followed for 12 months. Figure 5 outlines the milestones of a pragmatic randomized controlled trial and implementation study. Study milestones are further detailed in the timeline (under Section E.1, Table 2).

Recruitment: We will recruit participants through the SLAAA's annual assessment of participants' health. We estimate more than 800 older adults will meet eligibility criteria.

Deliver intervention: Interventionists will use a manualized protocol to deliver the intervention.

Follow-up: We will follow participants monthly using a highly successful calendar journal

technique that has demonstrated a 99% response rate in previous studies. Dissemination: We will disseminate the program, manuals, and training programs using our advisory network.

Pragmatic trial designed for implementation and dissemination

300 community-dwelling older adults with high risk of fall
-Baseline assessment
-Randomization

Intervention (150)
Home hazard removal

Control (150)
usual care

12 month follow-up

12 month follow-up

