5.2 Study Enrollment Procedures

Study population, eligibility, and screening. The National Aging Program Information System (NAPIS) is a database of information collected annually by the AoA from state units on aging describing the general health, nutritional, financial, functional, and environmental status of an older adult. Missouri’s assessment (MA4) currently *includes an evidence-based fall-risk screening* as part of an extensive battery of standardized assessments. In the current cohort of 1,331 older adults screened in CY 2013 by SLAAA, the average age of the cohort is 77 years, 67 percent are female and 74% are African American. More than 25% reported a fall in the past 12 months, and 40% are “worried about falling.” The average score on ADL performance was 4 (range, 1–7); indicating moderate ADL impairment). We will recruit from this cohort of older adults who are “at high risk for a fall.”⁷⁹ We estimate more than 800 older adults will meet eligibility criteria in the cohort. ^{2,3} The SLAAA staff will identify potential participants and assist in recruiting participants at no cost

We will recruit 300 older adults, conduct baseline assessments, and randomize participants to receive the adapted program or usual care. Outcomes (falls, fall self-efficacy) will be assessed by a blinded evaluator at baseline and 12 months after intervention. Flow through the study is illustrated in Figure 5. All assessments and study visits will occur in participants’ homes.

Recruitment. We will randomly select a sample of older adults from the large observational cohort of older adults assessed annually by SLAAA via NAPIS as part of service delivery⁸⁰ and invite them to participate by telephone. Refusals will be tracked for attribution of cause.

Consent and enrollment. Consent will be obtained at the baseline home assessment visit. Potential participants will be provided with a study brochure and a copy of the large-print consent form. Scripted details of the project including the randomization procedure, study interventions, and follow-up procedures will be discussed (under Section C.2.c).

Randomization sequence generation, allocation concealment, and implementation.

Participants will be allocated using a 1:1 ratio via randomization sequences generated a priori using a computerized formal probability model. The allocation ratio will be maintained at periodic intervals. Groups will be balanced with regard to race (self-reported African American

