or “other”) and sex. Randomization sequence concealment will be achieved by the Research Electronic Data Capture (REDCap) system.⁸¹ After baseline assessment, the study coordinator will verify that all eligibility requirements are satisfied and then elicit treatment assignment.

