7.3.2.3 Baseline Assessment

Demographics. Demographic and other pertinent information, including assistance received, adaptive equipment usage, and falls, will be collected.

OARS ADL scale. The OARS ADL scale^[51] will be used to screen for functional performance. The OARS ADL has been validated for the older adult ED population^[52], is brief and easy to administer. Potential participants are asked about their ability to perform each of 14 activities. Responses are scored on a 0-2 scale, with higher scores indicating greater independence. Individuals who receive a score of 0 on one or more activities or a score of 1 on two or more activities will qualify for the study.

Falls Efficacy Scale-International (FES-I). The Falls Efficacy Scale-International (FES-I)^[53] will be used to assess participants’ self-efficacy in performing daily activities without falling. The FES-I has good test-retest reliability and validity and consists of a list of 16 daily activities (e.g., getting in and out of bed) on which respondents rate their confidence doing each activity without falling on a scale from 1 (very confident) to 10 (no confidence at all). Total FES-I score is the sum of each activity score, with higher scores indicating greater fear of falling.

Patient Reported Outcomes Measurement Information System (PROMIS) Global Scale. Self-rated health will be measured using the Patient Reported Outcomes Measurement Information System (PROMIS) Global Scale^[54] which measures general perceptions of health. We will use two scales: global physical health (overall physical health, physical function, pain, and fatigue) and global mental health (quality of life, mental health, satisfaction with social activities, and emotional problems). Reliability and validity of the scales have been established^[54, 55].

Westmead Home Safety Assessment (WeHSA). The Westmead Home Safety Assessment (WeHSA)^[57] will be used to identify the number of environmental hazards in all areas of the home (e.g., seating, bedroom, medication management) via 72 categories. Each category is specified with explicit descriptors to qualify a given hazard with a score of 0 for absent and 1 for present. Total hazards are summed.

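### Section 5.2 draws the treatment assignment after the baseline assessment and Section 7.3.2.2 draws it before; nothing in the protocol says which order governs

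*Combined protocol and SAP*

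**What the plan says.** Two versions of the randomization paragraph are in force. Section 5.2 (Study Enrollment Procedures, not the Process Evaluation section that bears the same number) ends: "After baseline assessment, the study coordinator will verify that all eligibility requirements are satisfied and then elicit treatment assignment". Section 7.3.2.2 (Randomization) ends: "The study coordinator will verify that all eligibility requirements are satisfied and then elicit treatment assignment prior to baseline assessment".

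Other text that bears on the order:

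- The Section 5.2 overview: "We will recruit 300 older adults, conduct baseline assessments, and randomize participants to receive the adapted program or usual care".
- The Section 4 flow diagram lists "Baseline assessment" directly above randomization.
- The 7.3.2 heading reads "Enrollment, baseline, randomization", but its subsections run enrollment, randomization, baseline.
- The Table 7.5 footnote says "randomization before T1". T1 is not a column of that table.

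The content of the baseline assessment also differs between sections. Section 7.3.2.3, which carries that title, opens with "Demographic and other pertinent information, including assistance received, adaptive equipment usage, and falls, will be collected". It goes on through OARS, FES-I, PROMIS and other instruments, and says of medications: "A medication inventory will be collected". Table 7.5 puts demographics, medication, FES, PROMIS, GDS and the falls behavioral scale at the consent visit, and OARS, POMA, the vision tests, WeHSA and others in the baseline column.

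**The concern.** Staff cannot follow both sentences, and the difference decides whether baseline data are collected before or after the arm is drawn. A covariate measured before allocation cannot be influenced by it. One measured afterwards can be, if the participant or the assessor knows the arm.

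Section 10.3 tests the intervention effect in a covariate-adjusted Cox model as well as by the log-rank test, and names mobility, ADL scores and visual acuity among its example covariates. OARS is also the baseline for the daily-activity outcome. At stake are the standing of those covariates as true baseline values and, if a qualifying rule were read after assignment, the set of randomized people who are analysed.

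**Working it through.** The plan gives no figure on this point, and the sample-size calculation does not depend on the order. The check is a comparison of texts and a count.

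**1. Can both sentences be true?** Only if baseline assessment means different things in the two sections. One could place assignment between the consent-visit and baseline columns of Table 7.5. No text states this. Section 5.2 says that consent is taken at the baseline home visit, and 7.3.2.1 says that it is taken at the first home assessment visit, so the two columns need not be separate visits. Even on that reading, everything in the baseline column follows allocation.

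**2. Does the footnote settle it?** If T1 is the baseline assessment, the footnote agrees with 7.3.2.2. If T1 is the first treatment session, it fits either order.

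**3. What falls after allocation if 7.3.2.2 is followed?**

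| Definition of baseline | Participant measures | Example Cox covariates affected (beyond age, race, sex) | Participant-reported baselines affected |
|---|---|---|---|
| Table 7.5 baseline column | WeHSA, S-MAST-G, ROM, strength, grip strength, near visual acuity, contrast sensitivity, POMA, falls, OARS = 10 | OARS, POMA, near visual acuity = 3 | OARS = 1 of 3 |
| Section 7.3.2.3 list | 13 entries, less SBT = at most 12 | medications, OARS, POMA = 3 | OARS, FES-I, PROMIS = 3 of 3 |

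The 13 entries are demographics with falls, OARS, FES-I, PROMIS, WeHSA, S-MAST-G, GDS-SF, SBT, medications, POMA, strength with range of motion, Pelli-Robson and the falls behavioral scale. SBT comes off because 7.3.1.1 and Table 7.5 place it at screening, and both versions of the paragraph require eligibility to be verified before assignment: 13 − 1 = 12. Demographics count only in part, because race and sex must be known for the balanced allocation. The fidelity grid is also marked in the baseline column but is not a participant measure. OARS and POMA are on both lists.

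**4. Is the arm shielded at baseline?** Section 5.2 promises a blinded evaluator at baseline, but names only falls and fall self-efficacy. Section 7.3.3.5 covers raters at follow-up. No text says that the arm is disclosed during the other baseline measures, and none says that it is withheld.

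**5. Which analyses are exposed?** The covariate-adjusted Cox test could be, through covariates recorded after allocation. The log-rank test uses no covariates. However, 7.3.2.3 attaches a qualifying rule to the OARS score that is absent from the criteria in Section 5.1. Applied after assignment, that rule could remove randomized people and so change the log-rank analysis set.

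**6. Does putting baseline first work as the plan stands?** Not fully. Section 7.3.3.1 has the therapist start the intervention in the course of the WeHSA, and Table 7.5 marks the WeHSA at both baseline and the treatment session. If one WeHSA serves both purposes, it cannot be completed before assignment and also be the start of treatment.

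**The case against.** The strongest reply is that 7.3.2.2 contains a slip and that the intended order is plain: Section 4 and Section 5.2 both put baseline first. This supports the direction of the fix but does not settle which text governs. The overview and the randomization paragraph of 5.2 are one section, and the 7.3.2 heading is reversed by its own subsections. Some material leans the other way: the fidelity grid is marked in the baseline column, and the intervention starts during an instrument that is also a baseline measure.

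T1 may also have been labelled in a diagram that is missing here. Section 7.2 ends in bare labels for the two arms, which could be its remains. That stands, so the claim is only that T1 is not defined in the available text.

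The consequences are conditional. Influence on a measure requires the arm to be known. Section 10.3 specifies no baseline-adjusted analysis of participant-reported outcomes, so harm there is hypothetical. The match of OARS to ADL scores and of POMA to mobility is reasonable but inferred, and the covariates are given only as examples. All of this stands and limits what can be concluded. None of it removes the contradiction.

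**Conclusion.** The contradiction is certain and should be fixed; its consequences are possible, not shown. Under 7.3.2.2, 10 participant measures (Table 7.5) or at most 12 entries (7.3.2.3) are recorded after allocation, including measures that correspond to three example Cox covariates on either list. This assumes that the table columns are as they appear in the available text and that the instruments match the covariates as above.

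A reader might infer four stronger things that the documents do not support:

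- That baseline is assessed with the arm known. No text says so.
- That the treatment effect is biased. Neither size nor direction can be derived.
- That all 13 entries of 7.3.2.3 follow allocation. SBT does not, and race and sex are already known.
- That participants would be excluded after randomization. The OARS rule is not among the Section 5.1 criteria, so this is only possible.

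The opposite inference, that the log-rank test is wholly safe, also goes too far, because of that same rule.

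**What to change.** 1. In 7.3.2.2, change the closing words so that assignment follows the baseline assessment, in line with Sections 4 and 5.2. This is a recommendation on method; the documents themselves do not settle the order.
2. Define T1 in the Table 7.5 footnote, or correct the footnote to match.
3. State one order, once: consent; all baseline measures (both the consent-visit and baseline columns of 7.5) and any eligibility check; REDCap assignment; treatment. Reconcile the OARS qualifying sentence in 7.3.2.3 with Section 5.1, so that it is clear whether it is an entry criterion.
4. Align 7.3.3.1 and the WeHSA and fidelity rows of Table 7.5, so that the baseline WeHSA score is recorded before assignment and the WeHSA that forms part of the intervention comes after it.

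The cost is wording in 7.3.2.2, 7.3.2.3 or 5.1, 7.3.3.1 and 7.5, and a small scheduling constraint where baseline and the first treatment session share a visit. No sample size or planned test changes.
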